5.3.7 Evaluation of Asymptomatic Patients

If any one of the following conditions are present on postnatal echocardiogram, ECG or Holter monitor, a cardiac assessment (Form 71) and cardiac physical examination (Form 79) will be performed by a pediatric cardiologist to determine the clinical cardiovascular status of the patient.

Echocardiogram findings requiring cardiac assessment and physical examination:

1. Fractional shortening < 20% or a change in fractional shortening >25%.
2. Pericardial effusion
 - a. Localized or circumferential with 5-10 mm diameter
 - b. Circumferential with > 11 mm maximal diameter
3. Valvular regurgitation
 - a. Aortic regurgitation, jet diameter > 3 mm
 - b. Pulmonic regurgitation, pathologic
 - c. Mitral regurgitation, jet diameter > 3 mm
 - d. Tricuspid regurgitation, jet diameter > 3 mm

4. Structural abnormalities
 - a. Ventricular septal defect
 - b. Atrial septal defect
 - c. Pulmonary stenosis
 - d. Patent ductus arteriosus after 2 months of age
 - e. Other significant structural abnormalities

ECG and/or Holter monitor findings requiring cardiac assessment and physical examination:

1. 2nd or 3rd degree heart block on ECG or Holter monitor
2. Supraventricular tachycardia
3. Atrial fibrillation
4. Atrial flutter
5. Ventricular tachycardia
6. Ventricular fibrillation
7. "Q" wave > 0.35 seconds, any leads
8. ST depression > 2 mm, any lead

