severe anemia (Lipshultz, Chanock, et al, 1989; Lipshultz, Sanders, et al, 1989A, 1989B). Abnormally elevated left ventricular mass, determined by echocardiography, demonstrated further serial increases in 73% of children with HIV infection (Lipshultz, Sanders et al, 1989C). This abnormal increase in left ventricular mass was more common in children with symptomatic HIV infection. Since changes in left ventricular function and mass occur frequently and may relate to clinical disease, an echocardiographic evaluation and a corresponding cardiac history and physical examination will be serially performed at 4 month intervals. A wide variety of conduction defects, voltage abnormalities compatible with chamber enlargement and dysrhythmias were noted by surface electrocardiography and holter monitoring in 93% of pediatric HIV patients (Lipshultz, Chanock et al, 1989). Serial electrocardiography has demonstrated progressive or new findings in 84% of these patients (Lipshultz, Chanock, et al 1989). Although electrocardiographic abnormalities were not related to HIV disease status, high grade rhythm disturbances were more common in patients with hyperdynamic left ventricular function (Lipshultz, Chanock, et al 1989; Lipshultz, Sanders et al, 1989A, 1989B). Hyperdynamic left ventricular function was observed in patients at all stages of HIV infection and was related to abnormal autonomic function in many cases (Lipshultz, Chanock, et al 1989; Lipshultz, Sanders et al, 1989A, 1989B). Therefore, the electrocardiogram and Holter monitor study are scheduled at yearly intervals. Cardiac catheterization with biopsy is performed as clinically warranted. Chest x-rays are utilized to assess the cardiac silhouette, pulmonary vascularity and upper airway obstruction (tonsillar or adenoidal hypertrophy) if possible with the frequency dictated by the pulmonary protocol. Molecular, histologic and gross anatomic pathologic assessment of endomyocardial biopsy and autopsy material are analyzed as available according to the pathology protocol.

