0	X	X	X	X	As clinically warranted	Per Pulmonary Protocol	Bx as clinically warranted Postmortem when available
4	X			X			
8	X			X			
12	X	X	X	X			
16	X			X			
20	X			X			
24	X	X	X	X			
28	X			X			
32	X			X			
36	X	X	X	X			
40	X			X			
44	X			X			
48	X	X	X	X			
52	X			X			
56	X			X			
60	X	X	X	X			
64	X			X			
68	X			X			
72	X	X	X	X			
76	X			X			

**Table 20
Schedule of Cardiac Studies for Group 11b Controls**

Months on Study	Cardiac History and Physical Examination	EKG	Molter Monitor	Echocardiogram	Catheterization with biopsy	Chest X-ray	Pathology - Molecular - Histologic - Gross Anatomic
0	X	X	X	X	As clinically warranted	Per Pulmonary Protocol	Bx as clinically warranted Postmortem when available
4	X			X			
12	X	X	X	X			
18	X			X			
24	X	X	X	X			
30	X			X			
36	X	X	X	X			
42	X			X			
48	X	X	X	X			
54	X			X			
60	X	X	X	X			
66	X			X			
72	X	X	X	X			
78	X			X			

BLANK PAGE

(Rev. 11/10/93)

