Videotape and stripchart or page print recordings and blood pressure data will be sent to a central analysis site (The Children's Hospital, Boston) for analysis of LV size, function, loading conditions and contractility as described in the following paragraphs. The central analysis site has previous experience with multicenter use of this method of analysis. The central analysis site has documented that single center computer analysis dramatically reduces interobserver variability of analysis, in addition to reducing the equipment costs. The central analysis site has an extensive preexisting set of normative data for comparative purposes in infants and children of ages similar to those to be enrolled in this study.

DATA ANALYSIS

2-D and Doppler Echocardiogram:

The 2-D echo and Doppler exam are reviewed for masses and effusion. Valve morphology and function is recorded. Qualitative assessment of the LV shape and regional function are made, especially in short axis views. If there is uniform function and the LV is circular in cross-section, then formal evaluation of LV function (described below) is performed.

LV Size, Function, Loading Conditions, and Contractility:

The indirect carotid pulse tracing as well as the LV echocardiogram, including the endocardial border of the septum and the endocardial and epicardial borders of the LV posterior wall are hand digitized on a microcomputer based

digitizing station using custom software. This system is programmed to adjust the sampling rate to 200 Hz which is adequate to obtain at least 50 non-aliased harmonics at heart rates less than 120 beats per minute. The q wave of the ECG complexes bounding the cycles to be used as well as the onset of A2 and the onset of the carotid upstroke and the dicrotic notch are identified. After data input, the pulse transmission delay is corrected by electronically aligning the dicrotic notch on the pulse tracing with the first high-frequency component of the aortic valve closure sound. From the digitized data the following instantaneous measurements are obtained by averaging 3 to 6 cardiac cycles: (1) pressure during LV ejection, calculated by assignment of diastolic pressure to the minimum and systolic pressure to the maximum of the pulse trace and calculation of intervening values by linear interpolation; (2) LV internal diameter; (3) LV posterior wall thickness; and (4) LV meridional wall stress, calculated throughout ejection according to Mirsky:

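### Two thresholds in the Section 5.3.7 trigger list do not work: effusions just above 10 mm fall in a gap, and the 0.35-second Q-wave limit is in effect inert

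*Protocol*

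**What the plan says.** Section 5.3.7 of the Protocol is a mandatory rule for asymptomatic patients. If any one listed finding is present, a cardiac assessment (Form 71) and a cardiac physical examination (Form 79) "will be performed by a pediatric cardiologist to determine the clinical cardiovascular status of the patient".

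Three entries matter here:

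- Echocardiogram item 2a, pericardial effusion: "Localized or circumferential with 5-10 mm diameter".
- Echocardiogram item 2b, pericardial effusion: "Circumferential with > 11 mm maximal diameter".
- ECG/Holter item 7, for the Q wave: "wave > 0.35 seconds, any leads".

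Separately from these triggers, Section 5.3.2 states for Group I, and by reference for Group IIa, that "an echocardiographic evaluation and a corresponding cardiac history and physical examination will be serially performed at 4 month intervals" and that "the electrocardiogram and Holter monitor study are scheduled at yearly intervals". Table 20 ("Schedule of Cardiac Studies for Group 11b Controls") sets out the visits for the uninfected controls. For effusion as a study outcome, Section 5.3.3 says "The 2-D echo and Doppler exam are reviewed for masses and effusion".

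**The concern.** A list of triggers should not let a more severe finding escape when a milder one is caught. Items 2a and 2b do that. The first stops at 10 mm, the second begins strictly above 11 mm, and the second drops localized effusions altogether. Item 7 has a different fault: its threshold is so long relative to the cardiac cycle of a young child that it can hardly ever be met.

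At stake is the one response the protocol requires when an abnormality turns up in a child without symptoms. Section 5.3.8 does not fill the hole, because it applies to symptomatic patients. No other section gives a different effusion size or Q-wave limit. Detecting disease before it is clinically evident is an overall goal (Section 2.1) and Objective O2 (Section 2.3). Effusion is not rare in the planning figures: Table 5 expects it in 10% of HIV-positive neonates and 26% at 2.5 years.

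**Working it through.** There is no sample-size or power figure to reproduce. The check applies the written rule to a range of values.

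**Effusion (inputs: items 2a and 2b).** On the plain reading, the size range in 2a applies to both forms. The rule is then: trigger if 5 ≤ d ≤ 10 mm in either form, or if d > 11 mm and circumferential.

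| Diameter (mm) | Circumferential | Localized |
|---|---|---|
| 4 | no | no |
| 5 | yes | yes |
| 10 | yes | yes |
| 10.1 | no | no |
| 10.5 | no | no |
| 11 | no | no |
| 11.1 | yes | no |
| 15 | yes | no |
| 20 | yes | no |

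Item 2a can also be read as any localized effusion, or a circumferential one of 5-10 mm. The localized column then becomes yes throughout, but the circumferential column does not change. The circumferential gap, above 10 and up to 11 mm, exists on both readings. In whole millimetres it is exactly 11 mm.

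**Q wave (input: 0.35 s from item 7).** R-R interval in seconds = 60 / rate. The rates are illustrative, since the protocol gives no heart-rate distribution.

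- 100/min: 60/100 = 0.60 s; 0.35/0.60 = 58%.
- 120/min: 60/120 = 0.50 s; 0.35/0.50 = 70%.
- 150/min: 60/150 = 0.40 s; 0.35/0.40 = 87.5%, about 88%.
- The limit equals the whole interval at 60/0.35 = 171/min.

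A Q wave is only the initial deflection of the QRS complex and cannot plausibly occupy such a share of the cycle.

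**Time to the next scheduled cardiac examination.**

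- Tables 18 and 19 (Groups I and IIa): months 0, 4, 8, 12 and so on to 76; every gap is 4 months.
- Table 20 (Group IIb controls): months 0, 4, 12, 18, 24 and so on to 78; the gaps are 4, then 8, then 6 months throughout.
- ECG: every 12 months in all three tables.

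**The case against.** The strongest reply has four parts.

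- **Character reading.** Each fault turns on very little: a greater-than sign in place of greater-or-equal, or one missing zero. The text was read from a PDF with visible errors elsewhere. A misreading is possible but not shown, and the greater-or-equal sign survives in Sections 5.1.4 and 5.3.3. With that sign, the circumferential gap would close in whole millimetres, but localized effusions above 10 mm would still be uncovered on the plain reading.
- **The Q-wave argument leans on physiology.** The protocol gives no normal Q duration and no intended limit, and ECG methods are delegated to a Manual of Operations that is not at hand. This is why no replacement value is proposed here. The cycle-length arithmetic is still enough to show that the printed value needs checking. The ECG audit in Section 8.3.1 covers artifact and amplitude, not wave duration, so it would not expose the problem.
- **Other safeguards.** Tables 8 to 11A schedule a routine cardiac assessment, Section 8.3.2.1 wants a physician echocardiographer present where possible, and Table 14 has general physical examinations at months 6 and 9, inside the 8-month cardiac gap. Figures 3 and 4 are not shown. These points stand and keep the consequence small. The routine provisions do not replace the finding-driven cardiologist assessment, and the protocol does not say who performs the routine cardiac examination.
- **The re-screen.** A single database query presumes that effusion diameter and Q-wave duration are stored as measurements. The protocol does not establish this. The correction of the list does not depend on it.

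**Conclusion.** The concern holds, as a minor fault stated with high confidence. The circumferential effusion gap, above 10 and up to 11 mm, follows from the text on either reading of item 2a. The gap for localized effusions above 10 mm follows on the plain reading only. The Q-wave item is in effect inert at the illustrative rates. That rests on the cycle-length arithmetic and on what a Q wave is. A decimal or unit slip is probable, but the intended value is not in the protocol.

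The loss is confined to the mandatory cardiologist assessment in response to the finding. Effusion as an outcome is read from the echocardiogram itself, so no analysis is affected. If the examination at the same visit prompts nothing further, the next scheduled cardiac examination is 4 months away in Groups I and IIa. In Group IIb controls it is generally 6 months away, or 8 months after the month-4 visit. The next scheduled ECG is a year away. The number of children affected cannot be derived, because the protocol gives neither an effusion-size distribution nor Q-wave data.

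**What to change.** 1. Restate item 2b as localized or circumferential, greater than 10 mm maximal diameter, and state that the 5-10 mm range in item 2a applies to both forms. Every effusion of 5 mm or more then falls in exactly one category. If the Cardiology Subcommittee meant any localized effusion regardless of size, item 2a should say so in words.
2. Have the Subcommittee verify the Q-wave value and unit against its source and re-issue item 7.
3. Have the Clinical Coordinating Center re-screen the echo and ECG measurements on file against the corrected list and return missed cases to the centers. If effusion size was recorded only in categories, the videotapes kept under Section 5.3.3 allow review.

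The cost is a short protocol correction and, where the measurements are stored, one database query. A few more cardiologist examinations would follow, of a kind the section already provides. No new test is needed.

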5.3.8 Evaluation of Patients with Possible Symptoms related to the Heart

The patients being studied are at a high risk of developing significant cardiac problems. Therefore, if any one of the following conditions are present in a symptomatic patient, a cardiac assessment and cardiac physical examination, to determine the cardiovascular status of the patient will be triggered.

1. Unexpected or unresponsive respiratory symptoms >7 days not thought to be due to lung disease
2. Persistent respiratory symptoms > 2 weeks in conjunction with documented pulmonary illness
3. Signs and/or symptoms of pericardial effusion or endocarditis
4. Signs and/or symptoms suggestive of congestive heart failure
5. Presence of frequent ectopy, unexplained "blue spells", unexplained seizures, unexplained syncope or significant autonomic dysfunction

The cardiac physical examination is to be performed by a pediatric cardiologist. If cardiac disease cannot be excluded, then further cardiac evaluation should be considered.

The following modifiers have known association with HIV and may be seen in HIV-infected patients with pericardial effusion, LV dysfunction or structural heart disease. These disorders can be detected, if present, by a P²C² postnatal echocardiogram evaluation. It is recommended that the following modifiers be considered at the time of the examination, as they may help direct the course of the evaluation (Figure 8, page 78b).

- Severity of intercurrent illness warrants hospitalization
- Evidence of clinical co-infections (e.g. EBV, CMV, MAI) present in symptomatic patient
- Evidence of HIV encephalopathy
- CDC-defined AIDS or severe immune dysfunction
- Antiretroviral therapy > 1 year and/or interferon therapy
- Known selenium or carnitine deficiency
- Past history of LV dysfunction or dilation, structural abnormality or pericardial effusion on echocardiogram

The following modifiers have known association with HIV and may be seen in HIV-infected patients with ectopy. Ectopy is likely to be detected by P²C² EKG and Holter monitor evaluations. It is recommended that these modifiers be considered at the time of the cardiac examination, as they may help direct the course of the evaluation (Figure 8, page 78b).

- Severity of intercurrent illness warrants hospitalization
- Evidence of clinical co-infections (e.g. EBV, CMV, MAI) present in symptomatic patient
- Evidence of HIV encephalopathy
- CDC-defined AIDS or severe immune dysfunction
- Therapy with IV pentamidine and/or ganciclovir
- Past history of LV dysfunction or dilation, structural abnormality or pericardial effusion on echocardiogram

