2.3 Secondary Hypotheses and Objectives

Hypotheses

- H3. The incidence of cardiovascular disease in HIV-infected children is increased with EBV and CMV infections.
- H4. The incidence of lymphoproliferative interstitial lung disease in HIV-infected children is increased with EBV infection.
- H5. HIV associated abnormalities of cardiovascular anatomy or function in the fetus persist into the neonatal period.
- H6. Identifiable cofactors of HIV-infection are associated with alterations in cardiovascular anatomy and function in the neonatal infant and child and include:
 - a. Pulmonary/systemic bacterial/viral infection
 - b. Altered immune system
 - c. Primary treatment of HIV-infection
 - d. Perinatal events (including intrauterine growth retardation, drug exposure, or infection) and neonatal illness
 - e. Growth failure
- H7. Identifiable cofactors of HIV-infection are associated with specific pulmonary** complications in the neonatal infant and child and include:
 - a. Altered immune system
 - b. Primary treatment of HIV-infection
 - c. Perinatal events (including intrauterine growth retardation, drug exposure, or infection) and neonatal illness
 - d. Growth failure

Objectives

- 02. To determine whether pulmonary and cardiovascular disease associated with vertically transmitted HIV infection is detectable with sensitive diagnostic methods before clinical signs and symptoms appear.
- 03. To estimate the recurrence rate of PCP.
- 04. To determine whether PCP accelerates the rate of decline of lung function and shortens the life span of HIV-infected children with chronic lung disease.

* Specific cardiovascular complications related to these hypotheses for the fetus are a-h, and for the postnatal infant and child are b-i:

- a. Altered umbilical blood flow profile
- b. Structural heart disease
- c. Altered myocardial performance
- d. Pericardial effusion with and without hydrops
- e. Arrhythmias
- f. Altered chamber size and wall thickness
- g. Cardiac valvular insufficiency or obstruction
- h. Cardiac tumors or masses
- i. Endocarditis (active or healed)

** Specific pulmonary complications related to these hypotheses are:

- a. Upper respiratory infection (rhinitis, pharyngitis, otitis, sinusitis)
- b. Fungal pulmonary infection
- c. Viral pulmonary infection
- d. Bacterial pulmonary infection
- e. Mycobacterial pulmonary infection
- f. Pneumocystis carinii pneumonia
- g. Lymphoproliferative lung disease
- h. Other interstitial lung diseases

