7.2 Statistical Methods

Specific statistical methods that will be used to evaluate each primary and secondary hypothesis or objective are described in this section.

The incidence, prevalence and recurrence rates of cardiac and lung complications (Objectives O1 and O3) will be summarized using confidence intervals on proportions. These rates will be determined at various time points (e.g., fetus, neonate and age 2.5 years); and will also be calculated in various subgroups such as Groups IIA and IIB or those children with and without certain cofactors (e.g., receiving drugs for treatment of HIV virus).

The primary hypotheses (H1 and H2) of comparing complication rates at specific time points in children with and without HIV-infection (Groups IIA and IIB) will be evaluated using the Mantel-Haenszel chi-square test stratifying on important potentially confounding variables such as IVDA of the mother. If there are several factors that need to be adjusted for simultaneously, a logistic regression analysis will be used to compare the rates with the factors as independent variables in the model along with an indicator variable representing group assignment. Similar analyses also apply to Hypotheses H3 and H4.

The persistence of cardiac abnormalities from the fetus to the neonate (Hypothesis H5) can be evaluated using McNemar's chi-square. If the abnormality is measured using a continuous variable (e.g., wall thickness from an echocardiogram), a paired t test or Wilcoxon signed rank test can be used.

To determine which cofactors are associated with cardiac or pulmonary abnormalities (Hypotheses H6 and H7), a logistic regression analysis will be done.

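### Cofactors tested in H3 and H6 may steer symptom-directed cardiac testing (section 5.3.8), and section 7.2 does not separate directed from scheduled findings

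*Protocol*

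**What the plan says.** Section 2.3 states H3 as "The incidence of cardiovascular disease in HIV-infected children is increased with EBV and CMV infections". H6 states that "Identifiable cofactors of HIV-infection are associated with alterations in cardiovascular anatomy and function", and its list of cofactors includes infection (a), altered immune system (b) and primary treatment of HIV infection (c).

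Section 5.3.8 sets five symptom or sign conditions: "if any one of the following conditions are present in a symptomatic patient, a cardiac assessment and cardiac physical examination" follow if one is met. If that examination leaves cardiac disease possible, further evaluation is to be considered; it is not mandatory. The section then gives two lists of modifiers, one for effusion, left ventricular dysfunction and structural disease (detected by echo) and one for ectopy (detected by EKG and Holter). For the first it recommends that "the following modifiers be considered at the time of the examination, as they may help direct the course of the evaluation", and it says the same in substance for the second. Among the modifiers:

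- "Evidence of clinical co-infections (e.g. EBV, CMV, MAI) present in symptomatic patient": in both lists; the exposure of H3 and part of H6a.
- AIDS by the CDC definition or severe immune dysfunction: in both lists; H6b.
- "Antiretroviral therapy > 1 year and/or interferon therapy": echo list only; H6c.

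For the analysis, section 7.2 says: "To determine which cofactors are associated with cardiac or pulmonary abnormalities (Hypotheses H6 and H7), a logistic regression analysis will be done". H3 is to be handled like H1 and H2, by a Mantel-Haenszel comparison of complication rates or by logistic regression. Section 7.1 names time-to-event analysis as the main type. None of these sections says whether an abnormality counts when it was found only at a symptom-directed study.

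**The concern.** If an exposure influences how often the outcome is looked for, and any detected episode counts, the exposed group will show more outcomes even when the exposure does nothing. Putting other covariates into the Mantel-Haenszel strata or the logistic model does not remove this, because the exposure itself drives the detection.

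What is at stake is the reading of H3 and H6. They are labelled secondary, but the opening of section 2 gives the secondary hypotheses the same scientific weight as the primary ones. A positive association between, say, CMV infection and arrhythmia could reflect biology, extra Holter recordings, or both, and the analysis as written could not tell them apart.

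One further feature points the same way. In Group I, CMV and EBV tests are done only when clinically warranted (Table 8, section 5.1.3), so recorded co-infection is itself tied to being symptomatic.

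**Working it through.** The plan gives no figure of its own on this point, so what follows is an illustration under no true association.

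**Inputs from the protocol**
- Children in the H3/H6 analyses: Groups I and IIa (end of section 7.2), expected 200 + 120 = 320 (section 4.2).
- Scheduled echoes to 2.5 years (Tables 18 and 19): months 0, 4, 8, 12, 16, 20, 24, 28, so m = 8.
- Scheduled Holters to 2.5 years: months 0, 12, 24, so m = 3.
- Rates at 2.5 years (Table 5): pericardial effusion 26%; rhythm disturbance 70-77%, of which 70% is used.
- Significance level 1%, two-sided (sections 4.2.3 and 7.1).

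**Assumptions, not in the protocol**
- The Table 5 rate is what the scheduled studies alone would find.
- Studies detect independently of each other, which suits transient findings and overstates the gain for lasting ones.
- A child counts once any episode is found.
- Each cofactor-positive child has k more studies than a cofactor-negative child over 2.5 years.
- Cofactor prevalence is 30% (96 v 224 children) or 50% (160 v 160).

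**Formulas**
- Per-study detection probability: p = 1 - (1 - r0)^(1/m), with r0 the Table 5 rate.
- Rate with k extra studies: r = 1 - (1 - p)^(m + k).
- Odds ratio: [r/(1 - r)] / [r0/(1 - r0)].
- Chance of a false finding: Φ((|r - r0| - 2.576 × SE0)/SE1), with SE0 pooled under equality and SE1 unpooled.

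**One extra echo.** p = 1 - 0.74^(1/8) = 0.0369. Then r = 1 - 0.74 × 0.9631 = 0.287, and the odds ratio is (0.287/0.713)/(0.26/0.74) = 1.15.

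**One extra Holter.** p = 1 - 0.30^(1/3) = 0.331. Then r = 1 - 0.30 × 0.669 = 0.799, and the odds ratio is (0.799/0.201)/(0.70/0.30) = 1.71. With 160 v 160, SE0 = 0.0484 and SE1 = 0.0481, so z = (0.0992 - 2.576 × 0.0484)/0.0481 = -0.53 and the chance of a false finding is 0.30. With 96 v 224 it is 0.22.

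| Study | Extra studies k | Rate, cofactor v none | Odds ratio | False findings at 1% level |
|---|---|---|---|---|
| Echo | 0.5 | 27.4% v 26% | 1.07 | about 1% |
| Echo | 1 | 28.7% v 26% | 1.15 | about 2% |
| Echo | 2 | 31.4% v 26% | 1.30 | about 6% |
| Echo | 4 | 36.3% v 26% | 1.62 | 25-28% |
| Holter | 1 | 79.9% v 70% | 1.71 | 22-30% |
| Holter | 2 | 86.6% v 70% | 2.76 | 74-85% |

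The contrast comes from the schedule: one extra study is an eighth more echo surveillance but a third more Holter surveillance.

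**The case against.** The strongest reply has four parts.

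*Symptoms open the work-up, not cofactors.* This is correct. A reader might infer from the modifier lists that co-infection or treatment triggers cardiac testing. The text does not say that: no cofactor is among the five conditions, every triggered child gets the same assessment and cardiologist's examination, and the modifiers only may help direct what follows. Figure 8, which sets out the algorithm, is not shown in the copy reviewed, so how they enter it cannot be checked. What remains is that further testing is discretionary and that the protocol recommends weighing these cofactors at that step. That is enough for testing to differ by cofactor, though not to show by how much.

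*Surveillance is uniform.* Also largely correct for echo. A structural lesion or a lasting change in chamber size will be seen at the next 4-monthly echo whatever the cofactor status. Transient effusions and rhythm findings are not protected in this way. Blinded central reading (section 8.3.2.2) covers how a study is interpreted, not how many are done.

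*Section 7.2 refers to specific time points.* That phrase describes H1 and H2 and reaches H3 only through the remark that similar analyses apply. It leans towards scheduled visits without saying so, and the H6 sentence has no such limit.

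*Which studies feed an outcome can be left to the SAP.* Silence alone would be no finding. Here the protocol itself writes the tested exposures into the guidance on further work-up, so the analysis has to deal with it somewhere.

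**Conclusion.** The point holds as an expected direction of bias in the H3 and H6 cardiac analyses, with a size that the documents do not fix. Cofactor-positive children can be expected to have more transient or rhythm abnormalities detected with no true association. For echo the effect is small unless extra testing is heavy: an odds ratio of about 1.15 and about 2% false findings for one extra study. For Holter, scheduled only yearly, it is material: about 1.7 and 22-30% for one extra recording. The antiretroviral modifier bears on the echo list only, so the Holter figures concern co-infection and immune dysfunction.

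These numbers rest on the assumed extra studies, independence between studies and Table 5 rates. Since only symptomatic children have directed studies, an average excess of one per cofactor-positive child may be more than occurs. It would go too far to conclude that H3 and H6 findings will be spurious, or that more abnormalities will certainly be found in cofactor-positive children; the wording of section 5.3.8 is too soft to support that.

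**What to change.** Flag each echo, ECG and Holter as scheduled (Tables 18 and 19) or symptom-directed. State in section 7.2 that the H3 and H6 cardiac analyses will be run twice, on abnormalities found at scheduled studies and on all abnormalities, and that an association seen only when directed studies are included will not be taken as evidence of a cofactor effect.

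The cost is one data item, if the forms do not already carry it, and one analysis statement. The scheduled-only analysis loses transient events, and events in children who die or miss the next visit; section 7.3 already recognises such loss as informative. For that reason it should not replace the all-studies result, and both should be reported. Nothing in the clinical work-up of section 5.3.8 needs to change.
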